12.2 Sample Size and Accrual Rate

Approximately 27 patients with unresectable or metastatic CCA and 27 patients with locally advanced or metastatic PDAC will be enrolled, with ORR as the primary endpoint. Enrollment will be carried out in 2 stages so that the study can terminate early if the combination of entinostat plus nivolumab is not sufficiently effective.

Simon's two-stage, minimax, design will be employed in each cohort to test the null hypothesis that the true ORR is 5% or less (not considered clinically compelling for this combination). In the first stage, 13 subjects will be accrued.

If there are no responders among the first 13 subjects, the study will be terminated for futility. Otherwise, 14 additional subjects will be accrued to target a total of 27 treated and response evaluable subjects. The null hypothesis will be rejected if 4 or more responses are observed in 27 subjects per each cohort.

The probability of stopping the trial early for futility is 51% if the true ORR is 5% or less. This design yields 80% power at a one-sided type I error rate of 5% when the true response rate is 20% The study may enroll 33 subjects per cohort to ensure 27 would be evaluable for the primary efficacy endpoint. We expect to enroll 4-6 patients per month. We estimate that we could reach the accrual goal within 1 year.

Any patient who comes off of study due to toxicity before completing the first cycle of treatment, without evidence of disease progression may be replaced.

12.3 Study Endpoints Analyses

12.3.1 Analysis of Primary Endpoints

The objective response rate defined as the proportion of response evaluable subjects who have a CR or PR using RECIST 1.1 at any time during the study.

The evaluable population includes all subjects who have completed at least one dose of entinostat..

An exact binomial test will be used to evaluate the primary question of whether the response rate for combination therapy exceeds the historic rate for the single agent. Response rate will be reported with exact confidence interval.

12.3.2 Analysis of Secondary Endpoints

- OS is defined as the duration of time from start of study treatment to time of death. For subjects lost to follow-up or whose vital status is unknown, every effort will be made to determine the date such subjects were last known to be alive. Such efforts may include phone calls, certified mail, and the checking of public records. Subjects who are alive or lost to follow-up as of the data analysis cutoff date will be right-censored. The censoring date will be determined from the date the subject was last known to be alive.
- PFS is defined as the time from cycle 1, day 1 of immunotherapy until first documented local progression or death due to any cause. Disease progression will be assessed using RECIST (version 1.1). Due to the expectation that some patients may experience delayed clinical responses to therapy, patients with disease progression by radiographic imaging or laboratory parameters during a 12-week evaluation period but without rapid clinical deterioration or significant change in performance status that requires additional immediate therapy may continue to receive treatment on study.

Subjects that meet the above criteria and continue on study therapy must discontinue treatment upon documentation of disease progression on the second scan. The date of progression will be backdated to the time of first RECIST criteria progression. Tumor assessments will be made using RECIST 1.1 and immune-related response criteria (irRC). Individuals will be censored at the date of the last scan for PFS if no event occurs.

Median time to event will be calculated and reported with confidence intervals.

Analysis of PFS will be restricted to evaluable individuals who complete at least one dose of entinostat, while the analysis of OS will be performed on all evaluable patients.

OS curves, OS medians with 95% CIs, and OS rates at 6, 12, 24 and 36 months with 95% CIs will be estimated using Kaplan-Meier methodology

PFS curves, PFS medians with 95% CIs, and PFS rates at 6, 12 and 24 months with 95% CIs will be estimated using Kaplan-Meier methodology.

• Duration of response (DOR) will be calculated for subjects who achieve a best overall response of CR or PR with entinostat in combination with nivolumab. For such subjects,

duration of response is defined as the number of weeks from the start date of PR or CR (whichever response is recorded first) and subsequently confirmed to the first date that recurrent or progressive disease or death is documented. In such cases, recurrent or progressive disease will be assessed relative to the smallest tumor measurements recorded since the start of study treatment. The primary analysis of duration of response will be based on the time point responses, best overall response, and PD status that are determined by the review of the investigator

DOR will be summarized descriptively using the Kaplan-Meier method with 95% confidence intervals (CIs)

• The safety analysis will be performed in all subjects who receive any amount of study drug. A baseline measurement and at least 1 laboratory or other safety-related measurement obtained after at least 1 dose of study treatment may be required for inclusion in the analysis of a specific safety parameter (e.g., lab shifts from baseline).

A complete list of all AE data will be provided along with an assessment of NCI CTCAE grade and relationship to study drug. The incidence of AEs will be tabulated by subgroups of interest (e.g. grade 3 or higher, organ class, relationship to study drug).

For analyses at the individual level, the highest grade and relationship to study drug will be assumed if multiple events have occurred.

Toxicity will be tabulated by type and grade and will be summarized with descriptive statistics. Other safety data will be assessed in terms of physical examination, clinical chemistry, hematology, vital signs, and ECGs. Negative binomial regression and Cox proportional hazards models will be used to assess the rate of AE and time to first toxicity, respectively.

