1.2 Secondary Objectives

- **1.2.1** To assess the safety and tolerability of entinostat plus nivolumab in patients with unresectable or metastatic cholangiocarcinoma and unresectable or metastatic pancreatic adenocarcinoma.
- **1.2.2** To assess the progression free survival (PFS) status of patients with unresectable or metastatic cholangiocarcinoma and unresectable or metastatic pancreatic adenocarcinoma treated with entinostat plus nivolumab at 6, 12 and 24 months.
- **1.2.3** To determine the overall survival (OS) status of subjects with unresectable or metastatic cholangiocarcinoma and unresectable or metastatic pancreatic adenocarcinoma treated with entinostat plus nivolumab.
- **1.2.4** To determine the overall survival (OS) status of subjects with unresectable or metastatic cholangiocarcinoma and unresectable or metastatic pancreatic adenocarcinoma treated with entinostat plus nivolumab at 6 months, at 1, 2 and 3 years.
- **1.2.5** To assess the duration of response among subjects who demonstrate an objective response to treatment with entinostat in combination with nivolumab.

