4. TREATMENT PLAN

4.1 Agents Administration

Treatment will be administered on an outpatient basis. Reported adverse events and potential risks are described in **Section 6**. Appropriate dose modifications are described in **Section 5**.

No investigational or commercial agents or therapies other than those described below may be administered with the intent to treat the patient's malignancy.

The cycle length is 28 days. Treatment will consist of the combination of entinostat and nivolumab. A lead-in of entinostat 2 weeks prior to combination therapy at the dose of 5 mg/weekly, will be incorporated to help determine the effect of entinostat on immune-related parameters in tumor biopsies.

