8.2 Definitions

Evaluable for toxicity: All patients will be included in the toxicity summaries, from the time of their first treatment with study drug.

Evaluable for objective response: All patients must be accounted for in the summary of objective response. To formally classify a patient as RECIST-evaluable, only those patients who have measurable disease present at baseline (one of the eligibility criteria, **Section 3.1**) and start treatment (received at least one dose of entinostat) will be considered evaluable. These patients will have their response classified according to the definitions stated below (**NOTE**: Subjects who exhibit objective disease progression prior to the end of cycle 1 will also be considered evaluable.)

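### The Cox model for time to first toxicity has no covariate or comparison, so it gives no hazard ratio and no risk over time, and the safety tables are not split between the entinostat lead-in and the combination

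*Combined protocol and SAP*

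**What the plan says.** The safety objective in Section 1.2.1 is "To assess the safety and tolerability of entinostat plus nivolumab in patients" with either tumour type. It is secondary and carries no hypothesis.

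Section 12.3.2 plans a full adverse event (AE) listing with grade and relationship to drug, incidence broken down by grade, organ class and relationship, and this summary: "Toxicity will be tabulated by type and grade and will be summarized with descriptive statistics". Where a patient has several events, the highest grade and relationship are used. One further sentence adds the models: "Negative binomial regression and Cox proportional hazards models will be used to assess the rate of AE and time to first toxicity, respectively". No covariate, definition of toxicity, time origin, censoring rule or exposure term goes with it.

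On who is counted and from when, Section 12.3.2 states: "The safety analysis will be performed in all subjects who receive any amount of study drug". Section 8.2 adds: "All patients will be included in the toxicity summaries, from the time of their first treatment with study drug". First treatment is entinostat alone, because Section 4.1 specifies "A lead-in of entinostat 2 weeks prior to combination therapy". Treatment phase is not among the planned breakdowns.

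**The concern.** A Cox model estimates the effect of covariates on a hazard. Here there is no comparator and no named covariate, so the one analysis assigned to the timing of toxicity has no stated estimand. A reader wanting to know how many patients have a severe toxicity by three or six months would not find it in the planned output.

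The way patients leave adds to this. Section 4.8 generally ends treatment at progression, and exits from progression or death are likely to be common in these previously treated patients. If the Cox model were swapped informally for one minus Kaplan-Meier, with those exits censored, the reported risk would exceed the proportion of patients who actually have the event.

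The second issue is phase. The objective concerns the combination, but the tables start at the first lead-in dose and their denominator includes anyone who stops before nivolumab. Rates of nivolumab-type toxicity would then be lower than among patients exposed to nivolumab, and lead-in events would sit in the same cells as later ones.

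**Working it through.** **Plan's own figures.** The safety section states none. The only design calculation is for response rate (Section 12.2), and it reproduces: early stopping under the null is 0.95^13 = 0.513 (stated 51%), exact two-stage power is 0.801 (stated 80%), and exact type I error is 0.0416 (ceiling 5%). Nothing below touches it.

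**1. Cox model without a covariate.** The partial likelihood is the product, over events, of exp(βx) for the patient with the event divided by the sum of exp(βx) over those at risk. With no x, each factor is 1/(number at risk), so the likelihood is a constant with no parameter. A simulated data set of 54 patients gives a fixed log value of -94.53. A baseline hazard of Nelson-Aalen type can still be recovered, but the plan does not say it will be reported.

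**2. Would naming cohort as the covariate rescue it?** Assume two equal cohorts, 54 patients in total, and a two-sided 5% test.
- Events for 80% power at a hazard ratio of 2: (1.960 + 0.842)² / (0.25 × (ln 2)²) = 65.3, so 66. That is more than 54 patients can supply as first events.
- Power at a hazard ratio of 2 is 44% with 27 events and 72% with all 54.

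A cohort contrast is possible but imprecise, and it does not describe how safe the regimen is.

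**3. Negative binomial model.** This needs no covariate. In simulation, an intercept-only fit with log time as offset recovered a true rate of 0.030 per day as 0.025 (95% CI 0.017 to 0.037). It becomes a rate per unit of exposure only if the offset is used, and none is stated.

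**4. Censoring against competing exits (illustration).** The documents give no toxicity hazard. Assume constant monthly hazards: first grade 3 or higher toxicity λ = 0.10; leaving for progression or death h = 0.20 to 0.35.
- Exits censored: 1 - exp(-0.10 × 6) = 0.451.
- Cumulative incidence: λ/(λ+h) × (1 - exp(-(λ+h) × 6)).
  - h = 0.20: 0.333 × (1 - exp(-1.8)) = 0.278.
  - h = 0.35: 0.222 × (1 - exp(-2.7)) = 0.207.
- Death as the only competing event, using the second-line pancreatic median survivals of 3.3 and 5.9 months in Section 2.1.1: h = ln 2/3.3 = 0.210 gives 0.272; h = ln 2/5.9 = 0.117 gives 0.335.
- Toxicity risk continuing for one month after exit, with everyone alive at exit (an upper case): 1 - exp(-0.10) + exp(-0.10) × λ/(λ+h) × (1 - exp(-(λ+h) × 5)) = 0.329 for h = 0.20 and 0.275 for h = 0.35.

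**5. Lead-in and denominator (illustration).**
- Share of time on treatment spent in the lead-in, with w weeks on the combination: 2/(2+w), which is 33% at w = 4 and 8% at w = 24.
- Share of first events falling in the 14-day lead-in, at constant hazard with median time to first AE of m days: 1 - 2^(-14/m), which is 29% at m = 28 and 11% at m = 84.
- If k of 33 dosed patients in a cohort never start nivolumab, a rate over 33 is (33 - k)/33 of the rate among those exposed. The relative reduction is k/33: 3% for k = 1 and 15% for k = 5. Section 12.2 gives 33 as the maximum enrolment per cohort; k is an assumption.

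**6. Precision of the descriptive tables.** Exact 95% limits: 0 of 27 has an upper limit of 12.8%; 8 of 27 gives 13.8% to 50.2%. These proportions are usable, and no interval is planned for them.

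**The case against.** The strongest reply is that the objective is descriptive and the AE listing and tables already answer it; the models are one closing sentence. That stands. A reader might infer that the planned safety analysis cannot meet Section 1.2.1. The documents do not support this: crude incidence by grade, organ class and relationship is an absolute risk, and only the time dimension and the split by phase are missing. Nor does the criticism of the Cox model carry over to negative binomial regression, which yields a rate without a covariate.

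It can also be said that covariates exist. There are two cohorts, and objectives 1.3.1 and 1.3.5 relate baseline factors to toxicity. This is fair as to what could be fitted. But Section 12.3.4 specifies covariate-adjusted models for response only, and nothing links those factors to the Cox model. A Cox model that censors competing exits is also a legitimate cause-specific hazard model once a covariate is named; it still gives no absolute risk by itself.

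A reader might further infer that lead-in events will be reported as combination toxicity. No section says so. Section 6.3 records onset dates and relatedness to each drug separately, and an event should follow the drug it is attributed to. The any-dose population is conventional, consistent across Sections 8.2, 8.4 and 12.3.2, and defensible because the lead-in is part of the regimen. What remains is that no split is planned, and that keeping the highest grade per patient merges the two phases.

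Finally, the 45% describes a Kaplan-Meier-type estimate that the plan names for survival, progression and response duration but not for toxicity. Section 4.9 allows treatment after progression, and AEs are collected for at least 30 days after the last dose. Both narrow the gap.

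**Conclusion.** The point holds in two limited respects. The Cox model for time to first toxicity has no covariate or comparison, so as written it delivers no hazard ratio and no absolute risk over time. The any-drug tables pool the lead-in with the combination period and retain patients never given nivolumab, with no planned separation.

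The size is illustrative. The comparison of 45% with 21% to 28% at six months rests on assumed constant hazards and on a censoring analysis that the plan does not state. It should not be read as a bias in a planned result. With risk continuing one month after exit the cumulative incidence is 27.5% to 33%. The 3% to 15% dilution assumes 1 to 5 of 33 patients never reach nivolumab, a count the documents do not give.

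The missing event definition and exposure offset would, alone, be only missing detail. The change is worth making because a better-suited method is available from data already collected.

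**What to change.** In Section 12.3.2, for each cohort:

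- Replace the Cox model with the cumulative incidence of first grade 3 or higher toxicity, with a stated time origin. Treat death and off-treatment progression as competing events, the latter counted once the patient's AE collection window has closed. State where that window ends; Section 6.3 guarantees at least 30 days after the last dose.
- Keep negative binomial regression for AE rate, with log time at risk as offset.
- Keep the any-drug tables. Beside them, report AE proportions with exact 95% confidence intervals for the lead-in (all dosed patients) and from first nivolumab dose (all given at least one nivolumab dose), and state how many never received nivolumab.
- If a Cox model is still wanted, name its covariate and label it exploratory. The origin cannot be borrowed from progression-free survival, which runs from start of treatment in Section 8.3.6 and from cycle 1 day 1 in Section 12.3.2.

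The cost is some SAP wording and a few extra tables. Onset dates are already recorded, and the Study Calendar has toxicity assessments at lead-in Day -7 and at Day 1. The drawback is small counts in the lead-in tables.

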12.3.3 Data & Safety Monitoring

The PI and the study statistician will review the study as needed based upon rate of accrual for toxicity monitoring to identify accrual, and any endpoint problems that might be developing. The Sidney Kimmel Comprehensive Cancer Center Clinical Research Review Committee and Safety Monitoring Committee are responsible for reviewing accrual and safety data for this trial at least twice a year.

12.3.4 Analysis of Exploratory Endpoints

Exploratory correlative studies will be performed to investigate:

- To measure the baseline levels of immune markers including CD8+ T effector cells and CD4+FoxP3+ T regulatory cells, PD-L1 expression and tumor infiltrating lymphocytes (TILs), major histocompatibility complex (MHC) class I and II expression, and natural killer (NK) cell receptors and ligands expression and correlate these variables with treatment response and toxicity.
- To characterize changes in the immune markers described above after treatment
- To identify gene expression changes in malignant tissue after therapy, and complete gene set analysis to elucidate affected pathways
- To measure changes in circulating immune suppressor cells (MDSC, Treg) in peripheral blood by flow cytometry and test for association with response to therapy.

The overarching aim of these exploratory studies is to establish baseline levels and measure changes in immunological pathways after treatment. Little is known about baseline levels for these variables in Cholangiocarcinoma and Pancreatic Adenocarcinoma, let alone changes after treatment, and if the primary and secondary aims are successful, these investigations will establish a biological foundation on which to build in follow-up studies.

Immunological variables will be examined in plots and summary statistics, to characterize distributions, identify outliers and other potential problems in the data. Joint exploratory analysis will identify associations and potential interactions. Variables may be transformed on the basis of these investigations, to reduce skewness, minimize the influence of outliers and/or to regularize relationships between predictors and response for better model fit. Exploratory analysis of the molecular markers, including visualizations and statistical summaries such as hierarchical cluster analysis, heat maps, multidimensional scaling, and principle component analysis will offer important views of the structural characteristics of the expression data.

Response will be described categorically, and associations between response and immunological variables will be characterized, in each cohort, using multivariate logistic regression models, with adjustment for clinical and pathological co-variates that may be associated with response. Estimated effects will be reported with standard errors and confidence intervals.

We will fit empirical Bayes linear models [129] to identify genes for which expression is associated with response to treatment, controlling type I error at an FDR of <10%. Gene set enrichment analysis [130, 131] will be applied to the results to identify immune pathways that are significantly altered after treatment.

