1.3 Exploratory Objectives

- 1.3.1 To measure the baseline levels of immune markers including CD8+ T effector cells and CD4+FoxP3+ T regulatory cells, PD-L1 expression and tumor infiltrating lymphocytes (TILs), major histocompatibility complex (MHC) class I and II expression, and natural killer (NK) cell receptors and ligands expression and correlate these variables with treatment response and toxicity.
- 1.3.2 To characterize changes in the immune markers described above after treatment

1.3.3 To identify gene expression changes in malignant tissue after therapy, and complete gene set analysis to elucidate affected pathways

1.3.4 To measure changes in circulating immune suppressor cells (myeloid derived suppressor cells (MDSC), Treg) in peripheral blood by flow cytometry and test for association with response to therapy.

1.3.5 To assess the baseline characteristics of the subjects enrolled and to correlate these molecular and clinicopathologic criteria with treatment response and toxicity.

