It has been hypothesized that some tumor types with a more "immunogenic profile" that naturally attract T cell infiltration, are more likely to respond to checkpoint blockade. Evidence for this hypothesis is supported by data from studies in which a subset of lung adenocarcinomas with higher levels of somatic mutations had increased levels of inflammation-related gene expression and immune-checkpoint effector molecules, including PD-L1 and the evidence that the prevalence of neoantigens can be predictive of the response to checkpoint blockade with PD-1-targeted therapy in patients with non-small cell lung cancer (NSCLC), and with CTLA-4-targeted therapy in those with melanoma [21, 22].

Conversely, tumors with low neoantigen-presenting capacity, such as those that have a reduced number of potentially immunogenic somatic mutations or that do not present neoantigens through downregulated antigen processing, presentation or HLA expression might be overlooked by endogenous T cells [12, 23]. In this situation, antigen presentation and tumor-infiltrating lymphocytes (TILs) burden will likely be low, and immune-modulating mAbs alone would be less likely to generate a robust antitumor response, unless it is administered in the proper therapeutic context.

For instance, CCA and PDAC, has generally been considered a nonimmunogenic malignancy, insofar as tumor-infiltrating effector T lymphocytes do not represent a histopathologic hallmark of this disease. To date, studies of anti–CTLA-4 and anti–PD-1 mAbs have failed to demonstrate any objective responses in this setting, unless in the small fraction (about 3% of PDAC) of patients with hypermutated tumors and microsatellite instability [24].

Strategies to sensitize these tumors to checkpoint inhibition are warranted and the epigenetic modulation seem to play a very important role in this framework.

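### The marker–response model in section 12.3.4 is an adjusted logistic regression per cohort, but at the design's own response rates a full cohort averages about 1 to 5 responders, and no small-sample method or low-responder rule is given

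*Combined protocol and SAP*

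**What the plan says.** Objective 1.3.1 measures baseline immune markers, ending with "natural killer (NK) cell receptors and ligands expression and correlate these variables with treatment response and toxicity". Objective 1.3.4 and the second correlative hypothesis in section 9.1 also concern association with response.

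Section 12.3.4 gives the method. Response is treated as categorical, and "associations between response and immunological variables will be characterized, in each cohort, using multivariate logistic regression models". The models adjust for clinical and pathological covariates, and effects are to be reported with standard errors and confidence intervals. The section does not say which categories of response are meant; CR/PR is the likely reading from sections 1.4 and 12.3.1. It does not list or count the covariates, name the estimation method, or say what happens with no responders or very few.

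Section 12.2 fixes how many responders there can be. Each cohort uses a Simon minimax design to "test the null hypothesis that the true ORR is 5% or less". On stage 1: "If there are no responders among the first 13 subjects, the study will be terminated for futility". A cohort with at least one responder by then goes on to 27 evaluable patients in all. On the decision: "The null hypothesis will be rejected if 4 or more responses are observed in 27 subjects per each cohort".

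**The concern.** In a logistic model, the number of responders limits what can be estimated. With very few, some combination of marker and covariates often splits responders from non-responders perfectly, or nearly so (separation). The maximum-likelihood odds ratio then runs to zero or infinity, and its standard error and Wald interval mean nothing. Even with a finite estimate, a handful of events spread over several coefficients gives odds ratios that are biased away from the null and very imprecise.

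At stake is the part of the correlative programme that asks whether markers relate to response. Section 12.3.4 presents these studies as groundwork for later trials, so an extreme odds ratio produced by separation could be mistaken for a signal.

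**Working it through.** **Inputs from section 12.2:** 13 patients in stage 1, stop at 0 responders; 27 in total; null ORR 5%, alternative 20%; success at 4 or more.

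**Inputs assumed, because the documents give none:** response means CR/PR; one continuous marker plus one or three balanced binary covariates; no true effect; all 27 patients have marker data.

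**1. The plan's own figures.** Exact two-stage binomial calculation gives early stopping at 5% of 0.95^13 = 0.513, attained one-sided type I error 0.0416 and power 0.801. The plan states 51%, 5% and 80%, so its figures reproduce.

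**2. Responders per cohort.**
- Full cohort, 27 × p: 27 × 0.05 = 1.35; 27 × 0.20 = 5.4.
- Stopped at stage 1 with no responders, (1 − p)^13: 0.513 at 5%; 0.055 at 20%. No model can be fitted in these cohorts.
- Given that stage 1 is passed, the mean is 2.0 at 5% and 5.6 at 20%.

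**3. Distribution given that stage 1 is passed.** With q = 1 − p, P(x) = [C(27,x) p^x q^(27−x) − q^13 C(14,x) p^x q^(14−x)] / (1 − q^13).

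**4. Separation by responder count.** Simulated data sets of 27 were tested for complete or quasi-complete separation by linear programming.

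| Responders | P(x) at 5% | P(x) at 20% | No finite estimate, 1 covariate | No finite estimate, 3 covariates |
|---|---|---|---|---|
| 1 | 0.352 | 0.008 | 1.00 | 1.00 |
| 2 | 0.371 | 0.042 | 0.50 | 0.88 |
| 3 | 0.192 | 0.102 | 0.27 | 0.57 |
| 4 | 0.065 | 0.165 | 0.17 | 0.34 |
| 5 | 0.016 | 0.197 | 0.05 | 0.20 |
| 6 | 0.003 | 0.183 | 0.04 | 0.13 |
| 7 | 0.001 | 0.138 | 0.00 | 0.05 |

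A second run with 1,000 data sets per cell gave 0.50, 0.23, 0.11 and 0.06 (one covariate) and 0.88, 0.58, 0.36 and 0.18 (three) for 2 to 5 responders. The differences are of the size expected from simulation error.

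**5. Weighted over the design**, using P(x) from step 3 and the rates from step 4, with counts of 8 and 9 included:
- ORR 5%: 0.60 with one covariate, 0.81 with three.
- ORR 20%: 0.10 and 0.23.
- ORR 20% given success: P(4 or more, given stage 1 passed) = 0.801 / 0.945 = 0.848. The failing part is 0.046 with one covariate and 0.129 with three, so 0.046 / 0.848 = 0.05 and 0.129 / 0.848 = 0.15.

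Separate runs gave ranges of roughly 58–83%, 10–22% and 5–14% for these three cases. The two sets agree to within about two percentage points.

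**6. Sensitivity to the assumed predictors, given stage 1 passed, n = 27.**
- One or two continuous predictors plus two or three binary covariates, some with 30% prevalence, and with or without a 1 SD marker effect: 72–92% at 5% and 15–46% at 20%.
- Three to five continuous predictors only, no true effect: 24–51% at 5% and 2–8% at 20%.

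**7. Events per coefficient at the alternative.** One marker plus three covariates: 5.4 / 4 = 1.35. One marker plus one covariate: 5.4 / 2 = 2.7.

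**The case against.** The strongest reply is that the analysis is exploratory and that section 12.3.4 values it mainly if the primary and secondary aims succeed. A successful cohort has at least 4 responders, and the model then usually has a finite estimate. The plan also has other routes: plots and summaries, and empirical Bayes linear models for gene expression, which do not suffer logistic separation. All of that stands, and it rules out several stronger readings.

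- A reader might infer that the model cannot answer the question even if the trial succeeds. The figures do not support that: separation given success at 20% is about 5–14% under the stated assumptions. What remains there is overfitting.
- A reader might take 5% and 20% as the rates the trial expects. They are the null and the alternative; no expected rate is stated.
- A reader might cite section 2.2, where earlier antibody studies "have failed to demonstrate any objective responses in this setting", as evidence that there will be almost no responders. That sentence goes on to except hypermutated tumours, and section 2.4 reports a 17% ORR in PD-L1-positive cholangiocarcinoma.
- A reader might compute the chance of no responder at 5% as 0.95^27 = 25%. That ignores the stop at 0 of 13; under the design it is 51%.
- A reader might infer that the three mandatory biopsies rest on this objective. Section 9.1 also gives mechanism, effect on the tumour microenvironment and primary resistance. Objectives 1.3.1 and 1.3.4 use baseline markers and blood, so missed later biopsies do not directly reduce their data.

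The reply leaves the gap itself in place: plural covariates, a separate model per cohort, promised intervals, and no rule for a cohort with 0 to 3 responders.

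**Conclusion.** The point holds for the response-association model only. Near the null, the stated method will usually be unfittable or give no finite estimate: about 51% of cohorts stop with no responder, and roughly 58–83% of the rest separate. At the alternative, outright failure is a minority outcome (10–22% of cohorts that pass stage 1), but 1.35 to 2.7 events per coefficient cannot support a marker plus adjustment.

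The responder counts follow directly from section 12.2. The separation rates rest on the assumed number and type of predictors, on CR/PR as the outcome and on maximum likelihood, none of which section 12.3.4 states. They move substantially with those choices. The primary test, its error rates and the aims on baseline levels and marker change are unaffected.

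**What to change.** In section 12.3.4:

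1. State the response coding (CR/PR, or whichever other categories are meant).
2. Fit one immune marker at a time by Firth-penalised or exact logistic regression, in each cohort and pooled over cohorts with stratification or a cohort term.
3. Report only descriptively any cohort with fewer than 3 responders, including one stopped at stage 1.
4. As a supplementary analysis, report the rank correlation of each marker with best percent change in the sum of target-lesion diameters. Rank as worst the patients with no post-baseline scan because of progression or death. Use rank methods only: the worst-rank convention supplies no value for a linear regression.

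The cost is analysis wording; target-lesion diameters are already collected under section 8.2. The price is less covariate adjustment, and percent change ignores new and non-target lesions, so it should supplement response and not replace it. Penalised or exact methods make the estimates usable, but intervals from a handful of responders will still be wide and should be reported as such.
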